9. WHO Recommendations for the Prevention and Treatment of Postpartum Haemorrhage. Geneva: World Health Organization; 2012.
10. WOMAN Trial Collaborators. Effect of early tranexamic acid administration on mortality, hysterectomy, and other morbidities in women with post-partum haemorrhage (WOMAN): an international, randomised, double-blind, placebo-controlled trial. Lancet. 2017 Apr 26.

Research Design:

a. General Approach: Prospective Cohort study

b. Description: Phase 4

c. Methods: One Arm

d. Statistical Analysis:

- SPSS software will be used for our statistical analysis. Normal distribution will be assumed given the intended number of patients for analysis. Categorical variables will be analyzed using the Chi-square test. The t-test will be utilized for the comparison of continuous interval data.

-Using postpartum hemorrhage rate of 2.86% (institutional data), and a desired impact of reducing the hemorrhage rates by 50% after implementation of the new protocol, then 890 subjects would need to be recruited to answer the question.

e. Safety Analysis Plan:

- Data collection for each participant will occur in real time during pre and post delivery times, therefore safety monitoring of the patient and data will be simultaneous.
- A Research monitor has been appointed to oversee the safe and ethical conduct of the study. Additionally, the Research Monitor will provide review and comment on any adverse events. The Research Monitor is not a member of the investigative team. The role of the Research Monitor is as follows:
 1. monitor the consent process to ensure an absence of coercion
 2. monitor data collection/clinical outcome
 3. review all adverse event reports with comments from the PI and forward to the IRB with his/her own comments. Adverse events must be received by the IRB within 5 business days of occurrence or reporting (within 24 hours for serious adverse events)
 4. ensure the inclusion/exclusion criteria are followed
 5. review data security measures
- Any emerging safety concerns to include any adverse event rate higher than this institution's historical average will result in a halt to the study.

Subject Population:

Pregnant women presenting for delivery at NMCSO

a. Exclusion/Inclusion criteria:

Exclusion:

- a. Age less than 18 years
- b. Planned cesarean hysterectomy
- c. Current anticoagulant use
- d. Subarachnoid hemorrhage
- e. Any active/current intravascular clotting (i.e. venous thromboembolic events)

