 2. For patients that present for delivery at a gestational age less than 34 weeks, it will be recommended that they discard their breast milk until 24 hours after their last TXA administration.
 3. Order TXA for patient in ESSENTRIS
 4. RN to pull TXA from Pyxis and put in patient's room
 5. TXA per protocol (see supplement A)
 6. The use of additional uterotonics or single additional dose of TXA is at the discretion of the delivering provider
 7. For patient monitoring protocol please see Supplement B.
 8. All neonates are monitored for a minimum of 24 hours either by the NICU or the Newborn Nursery. Vitals are taken every four hours. Weights and bilirubin levels are obtained daily. Daily physical exams are performed.
3. Data collection
 1. Participants will be assigned an individualized subject number upon their enrollment to the study.
 2. Participants will be followed from their enrollment into the study until six weeks postpartum.
 3. An Excel spreadsheet will be used to collect the variables as listed above.
 4. Once the variable collection is complete, the information will become de-identified.

5. Chart review will be performed to estimate institutional rates of the secondary outcomes in the 12 months preceding the initiation of the protocol.
4. Data Analysis
 1. SPSS software will be used for our statistical analysis. Normal distribution will be assumed given the intended number of patients for analysis. Categorical variables will be analyzed using the Chi-square test. The t-test will be utilized for the comparison of continuous interval data.
 2. Using a postpartum hemorrhage rate of 2.86% (institutional data), and a desired impact of reducing the hemorrhage rates by 50% after implementation of the new protocol, then 890 subjects would need to be recruited to answer the question.
 3. The secondary outcomes will also be tested against institutional rates. Institutional rates will be estimated by record sampling done at the time of data collection.

Experimental Procedures:

See supplement A

Research materials collected:

Variables to be collected:

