Rates of hysterectomy – the number of patients requiring hysterectomy divided by the total number of deliveries

Admission to the Intensive Care Unit (ICU) - the number of patients requiring admission to the intensive care unit secondary to excessive blood loss divided by the total number of deliveries

Neonatal outcomes – incidence of fetal anemia, infection, hyperbilirubinemia, neurologic outcomes, and neonatal intensive unit admissions

Maternal mortality – incidence of mortality

Additionally, postpartum hemorrhage risk assessment will be utilized to stratify patients with regard to primary and secondary outcomes.

- Patients will be risk stratified to one of three risk categories depending on admission and intrapartum risk factors
 - High Risk Factors:
 - Placenta previa/ low lying placenta
 - Suspected accreta or percreta
 - Platelet count <70,000
 - Active bleeding
 - Known coagulopathy
 - Two or more medium risk factors
 - Medium Risk Factors:
 - Prior cesarean delivery, uterine surgery, or multiple laparotomies
 - Multiple gestation
 - > 4 prior births
 - Prior obstetric hemorrhage
 - Large myomas
 - EFW >4000
 - BMI > 40
 - Hct < 30%
 - Chorioamnionitis
 - >24 hours on Oxytocin
 - Magnesium sulfate
 - Low Risk: all patients not falling in the medium or high risk categories

Importance to Navy Medicine:

Beyond the potential impact that this study has in the reduction of maternal morbidity and mortality, it can also allow for perspective into resource management. Some of the Navy Military Treatment Facilities (MTFs) have limited blood bank stock, and massive hemorrhages requiring ongoing transfusion of products can quickly deplete the entirety of the supply. If we can find a solution that will reduce the number of instances where transfusion is necessary we can help to preserve limited resources. Likewise, this preventive measure will also have the potential to (cost) reduce the need for additional uterotonics, personnel, supplies and ICU beds.

There will be no collaboration with outside institutions.

Supplement A: TXA Protocol Administration (Modified from the NMCS Maternal Child Executive Committee's Policy)

1. TXA comes in a 1000 mg/10 mL vial. Nursing staff will pull this from the Pyxis at the same time they bring Oxytocin into the L&D room.
2. Add 1000 mg (or 1 vial) of 1000 mg/10 mL to 100 mL normal saline (100 mg/mL)
 - a. Bolus: 1 gram IV over 10 minutes
 - i. Set infusion pump rate to 600 mL/hr

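### The plan prescribes chi-square for every categorical outcome and gives no small-count method for rare secondary outcomes such as death, hysterectomy, reoperation and ICU admission

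*Combined protocol and SAP*

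**What the plan says.** Under Research Design, d. Statistical Analysis, and again under Study Procedures, 4. Data Analysis, the only test for categorical data is chi-square: "Categorical variables will be analyzed using the Chi-square test". The reason given for large-sample methods is the size of the cohort: "Normal distribution will be assumed given the intended number of patients for analysis".

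The design has a single arm ("Methods: One Arm"), so the comparator is historical. Study Procedures, 4. Data Analysis, item 3 states: "The secondary outcomes will also be tested against institutional rates". The source of those rates is described twice. Item 3 continues: "Institutional rates will be estimated by record sampling done at the time of data collection". Study Procedures, 3. Data collection, item 5 says: "Chart review will be performed to estimate institutional rates of the secondary outcomes in the 12 months preceding the initiation of the protocol". Neither place says how many records will be read, or whether the resulting rate is treated as a known constant or as a second sample.

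The Secondary outcomes section lists maternal mortality, hysterectomy ("the number of patients requiring hysterectomy divided by the total number of deliveries"), ICU admission because of excessive blood loss, and return to the operating room after cesarean, the last with cesarean deliveries only as denominator. No exact test, minimum expected count or descriptive-only rule appears.

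**The concern.** The number of events, not the number of women, decides whether the chi-square approximation is adequate. A cohort of 890 is large for an outcome near 3%, but not for one expected once or not at all.

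The rare outcomes here are among those a reader would weigh most heavily for a drug given at all deliveries. A p-value below 0.05 for one or two hysterectomies or ICU admissions could be reported as a finding when an exact calculation shows nothing unusual. If the historic records contain no event, a chi-square against that rate cannot be computed, and the plan offers nothing in its place.

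**Working it through.** **Inputs.** From the documents: n = 890, hemorrhage rate 2.86%, target reduction 50% (so 1.43%), chi-square for categorical outcomes. Assumed because the documents are silent: two-sided 5% level, 80% power, the expected counts E of the rare outcomes, and the historic sample sizes.

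**1. The plan's own figure.** For one proportion against a fixed rate:

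n = [1.960·√(0.0286×0.9714) + 0.842·√(0.0143×0.9857)]² / 0.0143² = (0.3267 + 0.0999)² / 0.000204 ≈ 890.

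The stated 890 is reproduced. One-sided 5% with 90% power gives 888.8, so level and power are not uniquely identified. A two-group comparison at two-sided 5% and 80% power would need 1,611 per group. The sample size therefore treats the institutional rate as a known constant.

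**2. Primary outcome.** Expected hemorrhages: 890 × 0.0286 = 25.5. The exact size of the chi-square test is 4.3% (1.7% low side, 2.6% high side), so the approximation is adequate here.

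**3. Rare outcomes against a fixed rate.** With x events, the statistic is (x − E)² / [E(1 − E/890)], significant above 3.84.

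- E = 0.1, x = 1: 0.81 / 0.09999 = 8.10, p = 0.004. Exact P(X ≥ 1) = 0.095.
- E = 0.5, x = 2: 2.25 / 0.4997 = 4.50, p = 0.034. Exact P(X ≥ 2) = 0.090.
- E = 0.2, x = 1: 0.64 / 0.19996 = 3.20, not significant, so two events are needed and the error falls sharply.

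Summing binomial probabilities over the rejection region gives the true error at nominal 5%:

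| E in 890 | Fewest events declared an excess by chi-square | Chi-square error | Exact binomial error |
|---|---|---|---|
| 0.1 | 1 | 9.5% | 0.5% |
| 0.2 | 2 | 1.75% | 1.75% |
| 0.5 | 2 | 9.0% | 1.4% |
| 1 | 3 | 8.0% | 1.9% |
| 3 | 7 | 3.3% | 3.3% |

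The chi-square error is a sawtooth. For E from 0.01 to 1 it runs from 1.0% to 16.1%, peaking near E = 0.175.

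**4. Direction, fixed rate.** Zero events gives the statistic E / (1 − E/890). This exceeds 3.84 only if E > 3.8415 / (1 + 3.8415/890) = 3.825, about 3.83 events or a rate of 0.43%. Below that, every rejection is an excess and no result can show a reduction.

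**5. Historic records as a second group.** Two-sample chi-square with 1 event expected in the 890 and the same true rate in both groups:

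| Historic records (assumed) | True error | Direction |
|---|---|---|
| 300 | 1.9% | all towards benefit |
| 890 | 1.4% | split evenly |
| 3,000 | 3.9% | nearly all towards harm |
| 4,000 | 5.1% | all towards harm |

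**6. No historic event.** The fixed-rate expected count is then 0, the statistic divides by zero, and no test is available.

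**The case against.** The strongest reply has four parts.

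First, the event counts are assumed. This stands: the documents give no institutional rate for any of these outcomes, and ICU admission would escape the one-sided result if its rate exceeded about 0.43%. Low counts are still plausible. Hemorrhage itself gives only about 25 cases, planned cesarean hysterectomy is excluded, and reoperation uses a smaller denominator.

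Second, a reader might infer that chi-square generally inflates the error here. It does not. Over expected counts from 0.01 to 3.00 in steps of 0.01, the mean error is 4.5%, and it is below 5% at 66% of the points. The fault is that the error is erratic and depends on a rate nobody has stated.

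Third, a reader might infer that the error is all on the side of harm. That needs a fixed comparator rate with fewer than about 3.83 expected events, or a large historic sample. The plan leaves the two-group reading open, and with 300 records the error runs the other way. The one-sidedness also comes from sparse data rather than from chi-square: the exact test has it too at 3.5 expected events or fewer.

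Fourth, the consequences are bounded. These are secondary outcomes, and the halt provision in the Safety Analysis Plan compares adverse event rates with the historical average without using a p-value. This also stands. What remains is that the plan commits to testing these outcomes and names a method that can give wrong p-values for them.

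**Conclusion.** The point holds in a limited form: the plan needs a small-count method for its rare secondary outcomes. On the assumption of about 0 to 3 expected events in 890, the prescribed test has a true error anywhere from about 1% to 16% against a fixed rate, and single results can be badly misstated (p=0.004 where the exact value is 0.095). If the records form a second group, neither the size nor the direction of the error can be given until the record count is fixed. The documents do not support a claim of general inflation or of systematic false signals of harm. The primary analysis and the halt provision are untouched. The change is worth making because it costs little and these outcomes will be read closely.

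**What to change.** In both statistical sections, add that for any categorical outcome with an expected cell count below 5, chi-square is replaced by an exact binomial test if the institutional rate is treated as fixed, or by Fisher's exact test if the historic counts form a second group. State which of the two applies and how many records will be read. Report death, hysterectomy, reoperation and ICU admission as counts over denominators with exact 95% confidence intervals, and say that they support no efficacy conclusion. If the historic records contain no event, a fixed rate of zero cannot be tested by either method; report both counts with their intervals. For scale, zero events in 890 gives an exact upper limit of 1 − 0.025^(1/890) = 0.41%.

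The cost is a few sentences in the plan. The price of the exact test is conservatism: its true error is 0.5% to 3.3% at the expected counts tabulated above. It keeps the error at or below 5% but does not remove the one-sidedness, so zero events still cannot show a benefit when few are expected.

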Age, race/ethnicity, DoD status, BMI, gestational age, # of fetuses, gravidity, parity, admission diagnoses, admission estimated fetal weight, intrapartum diagnoses, postpartum diagnoses, misoprostol use, oxytocin use, mechanical dilation, duration of labor, magnesium sulfate use, planned mode of delivery, mode of delivery, birth weight, indication for operative delivery, neonatal outcomes, maternal outcomes, admission to the intensive care unit, uterotonic use, mechanical tamponade, blood product transfusion, estimated blood loss, qualitative blood loss, cumulative blood loss, laboratory results, post-delivery laboratory results

Confounding variables:

Management of the 3rd stage of labor

Source of the data:

Outpatient records (AHLTA), Inpatient records (Essentris). As providers, the investigators have access to these systems as a standard of care for patients receiving care from investigator-providers.

Paper records created in the Labor and Delivery department during the course of a delivery.

The data collected will be measured against the historic PPH rates of NMCSO over a period of time to be determined.

Protection of Privacy:

Each participant will be given a unique study number. A master list with only the minimal Personal Identifiable Information (PII) needed for follow up and their study number will be kept in the PI's office on a CAC PIN protected computer in the PI's locked office. The master list will be used to track the results of the study participant's data collection.

An Excel spread sheet will be used to collect this information using only the participants unique study number and stored electronically on a CAC PIN protected computer in the PI's locked office.

All data and PII will be destroyed (shred or deleted) at the conclusion of this project.

Risks:

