To satisfy these two areas of responsibility, the research monitor may discuss the research protocol with the investigators, interview study subjects, and consult with others outside of the project about the research. In the event a problem is identified, they have authority to stop a research protocol in progress, remove individual subjects from a study, and take whatever steps are necessary to protect the safety and well-being of subjects until the IRB can assess the monitor's report.

Research monitors are required to promptly report their medical monitoring and oversight monitoring observations and findings to the IRB or other designated official.

Data Collection Sheets

See attached Excel spreadsheet.

Objectives:

The obstetrics literature to date focuses on TXA use prior to non-emergent cesarean delivery or in response to hemorrhage. Data is lacking in the area of prophylactic use prior to vaginal delivery. The aim of this study will be to assess the ability of TXA to prevent postpartum hemorrhage.

Primary Outcome:

To assess the efficacy of TXA in reducing the incidence of postpartum hemorrhage when given prophylactically prior to all deliveries.

The American Congress of Obstetricians and Gynecologists published 'ReVitalize' in 2014 that defined postpartum hemorrhage as blood loss of ≥ 1000 cc or blood loss accompanied by sign/symptoms of hypovolemia to include blood transfusion within 24 hours following the birth process (includes intrapartum loss).

[figure not shown]
For the purposes of this study, postpartum hemorrhage will be defined as a blood loss of ≥ 1000 cc in addition to all patients requiring blood transfusion (even if blood loss is less than 1000cc).

Secondary outcomes:

Estimated blood loss (EBL) – measured in cubic centimeters. EBL will be decided upon by the delivery provider. All delivering providers at this institution have received formal instruction on estimation of blood loss and a visual aid is available at every bedside and in the operating room (see below).

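### The 890 is sized as if the 2.86% historic haemorrhage rate were known exactly, but the comparator is an estimate from a period not yet chosen

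*Combined protocol and SAP*

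**What the plan says.** The design is a prospective cohort study with one treated arm (Research Design, items a and c). The sample-size statement is in Research Design, d. Statistical Analysis, and is repeated almost word for word in Study Procedures, 4. Data Analysis, item 2. It takes a PPH rate of 2.86%, sourced only to institutional data, and "a desired impact of reducing the hemorrhage rates by 50% after implementation of the new protocol", and concludes "then 890 subjects would need to be recruited to answer the question". Neither paragraph gives alpha, sidedness, power, a formula, or the numerator, denominator and period behind 2.86%.

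On the test, the plan says only "Categorical variables will be analyzed using the Chi-square test". It does not say whether this is a one-sample test against a fixed rate or a comparison of two groups.

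On the comparator, Source of the data says that the results will be "measured against the historic PPH rates of NMCSO over a period of time to be determined". Study Procedures, 3. Data collection, item 5 does set a look-back, but for "institutional rates of the secondary outcomes in the 12 months preceding the initiation of the protocol". The primary objective is "To assess the efficacy of TXA in reducing the incidence of postpartum hemorrhage when given prophylactically prior to all deliveries".

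**The concern.** A rate taken from a finite set of past deliveries has sampling error of its own. If 890 was obtained by treating that rate as a known constant, the sample size answers a different question from the one in Source of the data.

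Two things can follow, depending on how the Chi-square test is run:

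- **Historic deliveries as a second group.** Power is below what the known-rate calculation implies. A null result could then be misread as evidence that TXA does not halve PPH.
- **Historic estimate entered as a constant.** The test counts only the variability of the treated women, and the type I error generally exceeds its nominal level.

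While the window is open, neither quantity can be stated, and the comparator could be chosen after the PPH results are known. Few events decide the result: 890 × 0.0286 = 25.5 expected at the historic rate and 890 × 0.0143 = 12.7 at the target.

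**Working it through.** **Inputs from the plan.** p0 = 0.0286; p1 = 0.5 × 0.0286 = 0.0143; n = 890 treated; one arm.

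**Assumed, because the plan gives nothing.** Alpha 5%, two-sided or one-sided; historic deliveries N = 890, 2,000, 3,000, 4,000 or 10,000.

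**Step 1: reproduce 890.** For a one-sample test against a fixed rate,

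n = [(z_α·√(p0(1−p0)) + z_β·√(p1(1−p1))) / (p0−p1)]²,

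with √(0.0286 × 0.9714) = 0.16668 and √(0.0143 × 0.9857) = 0.11872.

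- Two-sided 5%, 80% power: (1.960 × 0.16668 + 0.8416 × 0.11872) / 0.0143 = 29.833; squared, **889.99**, so 890.
- One-sided 5%, 90% power: (1.645 × 0.16668 + 1.2816 × 0.11872) / 0.0143 = 29.812; squared, **888.77**, so 889 (computed with unrounded z values).

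A two-group calculation does not give 890. At 1:1 it needs 1,611 per group (two-sided 5%, 80% power) or 1,269 per group (one-sided 5%, 80% power).

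**Step 2: power of 890 if 2.86% were truly known.** By exact binomial calculation, the two-sided 5% test declares a reduction at 15 or fewer events, with power 78.9%. The one-sided 5% test does so at 17 or fewer, with power 90.6%.

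**Step 3: power if historic deliveries form a second group.** The test is the Pearson Chi-square without continuity correction, z = (x/n − y/N) / √(p̄(1−p̄)(1/n + 1/N)), with p̄ = (x+y)/(n+N). All binomial outcomes were enumerated with x at 1.43% and y at 2.86%.

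| Historic N (assumed) | 890 | 2,000 | 3,000 | 4,000 | 10,000 | Rate known |
|---|---|---|---|---|---|---|
| Power, two-sided 5% | 56.0% | 67.2% | 70.5% | 73.0% | 77.3% | 78.9% |
| Power, one-sided 5% | 67.4% | 78.5% | 82.1% | 83.7% | 87.2% | 90.6% |

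**Step 4: type I error if the estimate is entered as a constant.** Here q = y/N and z = (x/n − q) / √(q(1−q)/n), with both true rates at 2.86%.

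| Historic N (assumed) | 890 | 2,000 | 3,000 | 4,000 | 10,000 | Nominal |
|---|---|---|---|---|---|---|
| Two-sided total | 16.7% | 10.4% | 8.5% | 7.6% | 6.0% | 5% |
| of which false reduction | 6.4% | 3.9% | 3.2% | 2.9% | 2.3% | 2.5% |
| of which false increase | 10.3% | 6.5% | 5.3% | 4.7% | 3.7% | 2.5% |
| One-sided 5%, false reduction | 10.6% | 7.3% | 6.5% | 5.9% | 5.0% | 5% |

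The two-group test of Step 3, two-sided, holds its level over the same range, at 4.9% to 5.1%.

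**The case against.** The strongest reply is that nothing is miscalculated. The 890 follows from the plan's inputs by a standard formula, and a one-arm study measured against an institutional benchmark is a coherent design. On that reading the two-group power loss does not arise. The plan also states no power, so no printed claim is contradicted, and the size of the effect rests on assumed denominators. At 3,000 to 10,000 historic deliveries the two-sided power loss is about 8 down to 2 percentage points, and the false-reduction error, the tail that matters for the objective, is close to 2.5%. Finally, blood loss and transfusion, the two components of the study's PPH definition, are secondary outcomes, so the planned 12-month chart review would collect both.

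Much of this stands as a limit on size. The division is sound, the method behind 890 is inferred, only the two-sided setting gives 890 exactly, and most of the excess two-sided error is false increases.

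It does not remove the problem. If the benchmark is itself estimated from past deliveries, that reading is the case with inflated error. Both settings that come to 890 or within one of it assume a known rate, so the conclusion does not depend on which was used. The 12-month review is written for secondary outcomes, while Source of the data leaves the PPH period open. A long institutional record would help, but the plan does not commit to using one.

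**Conclusion.** The concern holds and should be fixed. The stated size fits a comparison with an error-free 2.86%, and the plan's comparator is an estimated historic rate of undefined period and denominator.

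How much this matters depends on that denominator. It is material for roughly 890 to 4,000 historic deliveries: two-sided power of 56% to 73% against 78.9%, or a false-reduction error of 6.4% to 2.9% against 2.5%. It is minor at 10,000 or more. On the one-sided reading, power is about 79% or better from 2,000 deliveries upward, against 90.6%. These figures assume true rates of 2.86% and 1.43%, 890 treated women analysed, and the alpha levels shown. The omission is certain; its size is conditional on the historic count.

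**What to change.** Revise both sample-size paragraphs (Research Design, d, and Study Procedures, 4, item 2) and bring Source of the data into line:

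1. State the alpha, sidedness and power actually used for 890, and that the calculation took 2.86% as known.
2. Name the primary analysis as a two-group comparison of treated with historic deliveries.
3. Fix the historic PPH window before the analysis, use all eligible deliveries in it, and report numerator and denominator. The 12 months already set for secondary outcomes is one option; a longer window loses less power.
4. Restate the power of 890 for that denominator.

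**Cost.** No additional patients are needed. The rewording is short, but record work increases: the plan foresees record sampling for the secondary rates, and applying the exclusion criteria to every historic chart in the window could be substantial. The power that can be claimed will be lower than the known-rate figure. A longer window recovers power but reaches back to a time when practice may have differed. These changes disclose any shortfall but do not close it. Restoring 80% two-sided power by enrolment would, by normal approximation, take about 1,399 treated women with 2,000 historic deliveries, or 963 with 10,000. Lengthening the window is the cheaper route.

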Informed consent will be obtained by members of the research team at any point during the subjects routine prenatal care visits.

Consent will only be obtained during a face-to-face communication in a confidential setting.

A member of the research team will provide a verbal and/or written information sheet giving a complete description of the rationale, goals, and requirements of the study. Participants will also be told of the volunteer nature of the study, and that they may cancel their participation in the study at any time, following the process outlined in the consent form.

The PI, AIs, or the research nurse will be available during the recruitment and enrollment phase of the trial. The PI/AI is available throughout the course of this trial. After reading the consent, having all questions answered to their satisfaction, and acknowledging understanding of what is involved in the trial, participants will be asked to sign the consent, along with the research team member obtaining the consent. A copy of the participant's signed consent will be given to them for their personal records.

All consents will include the participant's signature on the IRB-approved consent form. The participant will be given a copy of their signed consent form.

The original signed consent will be kept by the Clinical Research Nurse Coordinator in a locked cabinet in the office of the Clinical Research Nurse Coordinator.

Participants will be informed that they have the right to withdraw from this study at any time. If they decide to stop taking part in this study, they will be asked to tell the principle investigator as soon as possible.

Subject participation may be stopped without participant consent if remaining in the study might be dangerous or harmful in the investigator's opinion. It may also be stopped without participant consent if the military mission requires it, or if the participant loses the right to receive medical care at a military hospital.

Study Procedures:

1. Recruitment/Enrollment
 1. Identify subjects who meet inclusion criteria at prenatal registration, L&D tours, GDM classes, and on L&D
 2. Obtain written consent from potential participants after participant has had time to read, understand and comprehend
 3. "TXA Study Participant" to be added to problem list on hard chart, AHLTA template and ESSENTRIS intake
2. Implementation on L&D
 1. Re-identify patients on admission

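### The plan gives 890 as the number to recruit, but 890 is the number that must be analysed, with no allowance for women who leave between prenatal consent and delivery

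*Combined protocol and SAP*

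**What the plan says.** The study has a single arm ("Methods: One Arm"). The sample size rests on an institutional hemorrhage rate of 2.86% and a "desired impact of reducing the hemorrhage rates by 50% after implementation of the new protocol". From these the plan concludes that "890 subjects would need to be recruited to answer the question". The sentence appears under Research Design, item d (Statistical Analysis), and almost unchanged under Study Procedures, item 4 (Data Analysis). Neither place gives alpha, sidedness, power or an allowance for loss.

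The comparator is described under Source of the data: "The data collected will be measured against the historic PPH rates of NMCSO over a period of time to be determined". The named test is general: "Categorical variables will be analyzed using the Chi-square test".

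The Consent Process section says that consent is obtained "at any point during the subjects routine prenatal care visits". It also lets a woman withdraw whenever she wishes. The team may end her participation for safety, for the military mission, or "if the participant loses the right to receive medical care at a military hospital". Under Study Procedures, consented women have to be identified again when they are admitted. No section says that women who leave are replaced, that recruitment runs on until a set number of deliveries has been analysed, or who forms the analysis set.

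**The concern.** The primary outcome, hemorrhage by blood loss or transfusion, does not exist until delivery. A woman consented at a prenatal visit who leaves before then adds to the recruited count but may add nothing to the primary comparison. If 890 is the size the test needs, 890 recruited supplies it only when nobody is lost. At stake is the chance of detecting a true halving of the hemorrhage rate, and whether a reader can tell from the plan what that chance is.

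**Working it through.** **Inputs.** From the Statistical Analysis item: p0 = 0.0286, and a 50% reduction, so p1 = 0.0143 and the difference is 0.0143. The design is one arm against a historic rate, taken here as a fixed value. Alpha and power are not stated and are inferred by finding which values return 890. The loss rate is not stated; 5%, 10% and 20% are assumed.

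**Step 1: reproduce 890.** The one-sample normal formula is

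n = [z(alpha) × √(p0(1−p0)) + z(power) × √(p1(1−p1))]² / (p0−p1)²

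Here √(0.0286 × 0.9714) = 0.16668 and √(0.0143 × 0.9857) = 0.11872.

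- Two-sided 5%, 80% power: 1.95996 × 0.16668 = 0.32669 and 0.84162 × 0.11872 = 0.09992. Then n = (0.42661 / 0.0143)² = 889.99, which rounds up to 890.
- One-sided 5%, 90% power: 1.64485 × 0.16668 = 0.27416 and 1.28155 × 0.11872 = 0.15215. Then n = (0.42631 / 0.0143)² = 888.77, which rounds up to 889.

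The first matches exactly and the second comes within one. Neither contains a loss term, so on either reading 890 is a number to analyse.

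**Step 2: power when 890 are recruited and some are lost.** For the two-sided 5% reading, normal-approximation power is

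Φ{[0.0143 × √n − 0.32669] / 0.11872}

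The exact column is the binomial probability, at 1.43%, of no more events than the critical count. That count is the largest whose lower-tail probability at 2.86% is at most 2.5%.

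| Loss (assumed) | Analysed | Argument of Φ | Normal power | Critical count | Exact power |
|---|---|---|---|---|---|
| 0% | 890 | 0.842 | 80.0% | 15 | 78.9% |
| 5% | 846 | 0.752 | 77.4% | 14 | 76.4% |
| 10% | 801 | 0.657 | 74.5% | 13 | 73.9% |
| 20% | 712 | 0.462 | 67.8% | 11 | 67.7% |

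**Step 3: small losses.** By the normal formula, one loss (889 analysed) lowers power from 80.00% to 79.94%, about 0.06 points. Power first falls below 78% at 855 analysed, a loss of 35/890 = 3.9%. Exact power moves in steps and is not monotone: 78.9% at 890, 80.1% at 880 and 81.0% at 872.

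**Step 4: the alternative reading.** For one-sided 5%, replace 0.32669 by 0.27416. Normal-approximation power is then 90.0% at 890, 88.4% at 846, 86.4% at 801 and 81.7% at 712. The level is higher and the fall smaller, but the direction is the same.

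**The case against.** The strongest reply is that recruited is loose wording for analysed. The Statistical Analysis item itself speaks of the number of patients it means to analyse. Inclusion requires delivery at the centre, so a woman who delivers elsewhere might never count. Study Procedures also lists the labor and delivery unit as a place to identify subjects, so some women may join close to delivery with little time to be lost. The outcome comes from delivery records, so loss before the six-week visit need not remove it. The exits are permissions, and no loss rate is given.

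These points make a benign reading possible and show that the amount of loss is unknown. They do not displace a recruitment figure stated twice, or the sentence that places consent at prenatal visits.

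A reader might infer that the study falls short of its power as soon as a single consented woman is lost. The calculations do not support that. The normal-formula cost of one loss is trivial. On the exact method 890 is itself slightly under 80%, and some smaller numbers do better. A reader might also infer an arithmetic error; there is none, since 890 reproduces exactly. Nor can heavy loss be presumed, because nothing in the documents points to any particular rate.

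**Conclusion.** The concern holds in a limited form. The 890 is an uninflated analysed number labelled as a recruitment number, in a plan that consents women before delivery and names ways they can leave. Fewer than 890 evaluable deliveries is probable, not certain. On the reading that reproduces 890 exactly, a 5% loss costs about 3 points of power, 10% about 6 and 20% about 12 by the normal approximation.

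This rests on three assumptions: the inferred alpha and power, the assumed loss rates, and a historic rate treated as known without error. The last is favourable to the plan. The historic period is still open, and if that rate were estimated from a sample and compared by a two-sample test, 890 treated women would give about 55% power against an equal-sized historic group and 71% against one four times larger. That is a separate matter, but it means the figures in the table should not be quoted without their condition. The point should be corrected; it does not by itself undermine the study.

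**What to change.** In both places where 890 appears, restate it as the number of women who deliver at the site with hemorrhage status known. Beside it, give the alpha, sidedness and power from which it was derived.

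If recruitment stays at 890, add the loss the sponsor expects and the power that remains, with a note that this power assumes a fixed historic rate. On the two-sided 5%, 80% reading, that would be about 74% at 10% loss or 68% at 20%.

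If the sponsor would rather protect the power, recruitment of 890/(1 − loss) does so: 937 at 5%, 989 at 10% and 1,113 at 20%. This is optional.

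The restatement costs a sentence or two in each place and a less favourable stated power. It requires no added enrolment.
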